7.3 Study Milestones Timeline

The study milestone timeline presented below is based on the expectation that, following the initiation of the first site, the remaining study sites will be activated at a rate of approximately 3 per month, and the enrollment rate at activated sites will be approximately 2 subjects per month.

Table 7-1 **Study Milestones**

Key Milestone	Target Date
First Site Initiated	August 20, 2017
First Patient First Visit	September 20, 2017
Last Patient First Visit	February 20, 2020
Last Patient Last Visit	April 20, 2023
Database Lock	May 20, 2023
Submit PAS Final Report	July 20, 2023

Figure 7-1 **Study Design**

8 CLINICAL TRIAL OBJECTIVES

8.1 Primary Objective

To demonstrate the rate of clinically relevant complications associated with CyPass Micro-Stent placement and stability using the CyPass System (Model 241-S) as determined at 36 months in the post-market setting is less than the pre-specified performance target, which is based on experience with the CyPass Model E applier in the COMPASS (TMI-09-01) trial.

8.2 Study Endpoints

8.2.1 Effectiveness Endpoints

8.2.1.1 Primary Effectiveness Endpoint

There is no primary effectiveness endpoint for this study.

8.2.1.2 Secondary Effectiveness Endpoints

All secondary effectiveness endpoints will be evaluated at 36 months postoperatively.

- ≠ Mean change in IOP
- ≠ Proportion of subjects with IOP reduction $\geq 20\%$ while using the same or fewer topical ocular hypotensive medications
- ≠ Proportion of subjects who are not using ocular hypotensive medication with IOP ≥ 6 mmHg and ≤ 18 mmHg

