Visit 2 must occur 5-9 days postoperatively. Below is a list of study procedures to be undertaken at this visit. Ocular assessments will be conducted for the study eye only.

1. Document changes in concomitant medications.
2. Perform manifest refraction and record monocular BCDVA using an ETDRS chart at 4 meters.
3. Measure IOP with Goldmann tonometer between 8:00 and 10:00 am.
4. Conduct slit lamp examination.
5. Perform Gonioscopy (including Shaffer grading for all 4 quadrants) with goniophotography of CyPass location.

6. Record any adverse events and/or device deficiencies.

NOTE: SAEs must be entered into EDC within 24 hours of the Investigator's knowledge. Refer to Section 13 for further detail.

12.2.5 1 Month Follow-up (Visit 3)

Visit 3 must occur 21-35 days postoperatively. Below is a list of study procedures to be undertaken at this visit. Ocular assessments will be conducted for the study eye only.

1. Document changes in concomitant medications.
2. Perform manifest refraction and record monocular BCDVA using an ETDRS chart at 4 meters.
3. Measure IOP with Goldmann tonometer between 8:00 and 10:00 am.
4. Conduct slit lamp examination.
5. Perform Gonioscopy (including Shaffer grading for all 4 quadrants) with goniophotography of CyPass location.
6. Record any adverse events and/or device deficiencies.

NOTE: SAEs must be entered into EDC within 24 hours of the Investigator's knowledge. Refer to Section 13 for further detail.

12.2.6 3 Month Follow-up (Visit 4)

Visit 4 must occur 70-98 days postoperatively. Below is a list of study procedures to be undertaken at this visit. Ocular assessments will be conducted for the study eye only.

1. Document changes in concomitant medications.
2. Perform manifest refraction and record monocular BCDVA using an ETDRS chart at 4 meters.
3. Perform specular microscopy.

4. Measure IOP with Goldmann tonometer between 8:00 and 10:00 am.
5. Conduct slit lamp examination.
6. Perform Gonioscopy (including Shaffer grading for all 4 quadrants) with goniophotography of CyPass location.
7. Conduct dilated fundus examination (including C:D assessment).
8. Record any adverse events and/or device deficiencies.

NOTE: SAEs must be entered into EDC within 24 hours of the Investigator's knowledge. Refer to Section 13 for further detail.

12.2.7 6 Month Follow-up (Visit 5)

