15.4.2.2 Analysis Methods

Continuous endpoints will be summarized by number of observations (n), mean, median, standard deviation, minimum and maximum; binary endpoints will be summarized by numerator (number of eyes meeting the endpoint), denominator, and the proportion of ITT eyes meeting the endpoint. Denominators for adverse events, slit lamp findings, and other events will be the number of eyes in the ITT set. Denominators for data such as visual acuity and other subject data that is collected at protocol-required visits will reflect the number of eyes with non-missing data in the ITT set. Summary statistics will be presented at all postoperative visits for which the endpoint data are collected. Supportive analysis will be conducted using the DI analysis set for all secondary effectiveness outcomes.

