15.6 Handling of Missing Data

A tipping point analysis will be performed for the primary safety endpoint.

In addition, a comparison of baseline characteristics including age, gender, race, site, and baseline unmedicated IOP will be performed between those subjects who complete Visit 8 (36 Month Follow-up) and those who do not.

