15.8 Sample Size Justification

The performance target for the primary safety endpoint is 7.0%.

An evaluation of COMPASS (TMI-09-01) data showed that through 24 months of follow-up, there were two eyes with failures to implant and eight eyes with CyPass malposition events, respectively, corresponding to the above definitions. In addition, there were four eyes with documentation of three rings visible within the first postoperative week that likely would have undergone early secondary surgical intervention due to anterior CyPass positioning under the approach documented in the Instructions for Use (IFU). Inclusion of these cases would increase the number of observed events from 10 to 14 (3.74%, 95% confidence interval: 2.1% – 6.2%). Of note, not all investigators documented the number of rings visible in the early postoperative period because this was not a study requirement (data regarding the number of rings is recorded for only 96 subjects at 1 Day and 139 subjects at 1 Week), so this number likely underestimates the number of subjects who would have been candidates for early surgical re-intervention under the new criteria described in the IFU.

Based on these considerations, the “true” event rate is assumed to be 4.0%, and the performance target is set to 7.0%. The following assumptions were used for the sample size calculation:

- ≠ Type I error = 0.05
- ≠ one-sided alternative

With a sample size of 360 subjects in the final analysis (unilateral implants only) and a performance target of 7.0%, assuming a true event rate of 4.0%, there is 80% power to reject the null hypothesis based on a one-sided alpha = 0.05-level exact test for a single proportion.

To allow for attrition over this 36-month study, a cumulative rate of up to 20% of subjects lost to follow-up is assumed, corresponding to a targeted implantation of 450 eyes in 450 subjects to achieve at least 360 eyes with 36 months of follow-up.

Annex F of ANSI standard Z80.27-2014 refers to ensuring adequate sample size so that any adverse event of a given type that occurs in the population at a rate of 1% or greater is likely to be seen in the study. With 360 subjects, there is at least 97% probability that at least one adverse event will be detected, assuming a true rate of 1.0%. There is at least 95% probability if the true rate is 0.83%.

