2.1 Intention to Treat Analysis Set

The intention to treat (ITT) analysis set will be defined as the set of study eyes for which a CyPass Micro-Stent implant is attempted. The ITT analysis set will serve as the primary set for the safety and effectiveness summaries and analyses, as well as for all demographics, baseline, surgery, and study conduct summaries.

3 General Reporting Conventions

- ≠ All study eyes will receive the same treatment consisting of CyPass Micro-Stent implantation following uncomplicated cataract surgery. Therefore, summary tables will be presented for all subjects combined across all investigative centers.
- ≠ Available data at each assessment time point will be presented. No imputations will be made for missing data.
- ≠ Appropriate descriptive statistics will be computed and displayed (by assessment time point and other key variables as appropriate for both continuous and categorical variables as described below).

For continuous variables, descriptive statistics include n (number of subjects/eyes) with non-missing data, mean, standard deviation (SD), median, minimum and maximum values. The following number of decimal places will be used: mean and

median values to one more decimal place than the raw data; minimum, and maximum to the same number of decimal places as the raw data and SD to two more decimal places than the raw data.

For categorical parameters, the number and percentage of subjects/eyes within each category will be presented. The denominator for percentages will be based on the number of subjects/eyes with non-missing data appropriate for summary purposes. If a count of zero is obtained for categorical data, the zero count and percentage will still be displayed. Unless otherwise noted, percentages will be presented to one decimal place.

With the exception of the primary study endpoint, that is a one-sided test ($\alpha=0.05$), all other applicable confidence intervals (CI) will be at the $\alpha = 0.05$ (two-sided) level.

- ≠ Baseline is defined as the last assessments obtained prior to CyPass implantation surgery on Day 0.
- ≠ Change from baseline (pre-surgery) (where relevant) will only be summarized for subjects with both screening (pre-surgery) and post-op data for the relevant visit

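### The Month 36 mean IOP change is an available-case mean that ignores leavers' earlier IOPs; with up to 20% attrition assumed, it is biased if exit is related to pressure

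*Protocol*

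**What the plan says.** Protocol 8.2.1.2 and SAP 5.1.2 list mean change in IOP first among the secondary effectiveness endpoints: "All secondary effectiveness endpoints will be evaluated at 36 months postoperatively". That sentence fixes only the time point. Who enters the mean is set elsewhere:

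- SAP section 3 (General Reporting Conventions): "Available data at each assessment time point will be presented. No imputations will be made for missing data". The same section says change from baseline "will only be summarized for subjects with both screening (pre-surgery) and post-op data for the relevant visit".
- Protocol 15.4.2.2: denominators for data collected at protocol-required visits "will reflect the number of eyes with non-missing data in the ITT set".

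On attrition, Protocol 15.8 states that "a cumulative rate of up to 20% of subjects lost to follow-up is assumed", taking 450 implanted eyes to 360 with 36-month data.

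On missing data, Protocol 15.6 has two items. The first is "A tipping point analysis will be performed for the primary safety endpoint". The second compares baseline characteristics of subjects who do and do not complete Visit 8. Neither is an analysis of missing IOP.

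IOP is scheduled at all eight postoperative visits, seven of them before Month 36 (Protocol section 6 and 12.2.3 to 12.2.10).

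Protocol 12.4 asks sites to try to bring early leavers back for the Visit 8 procedures. Section 12.2.10 gives that visit the joint label of 36-month follow-up, exit and early exit, with a window of days 1050 to 1140. Neither document says whether an early-exit IOP outside that window counts as Month 36.

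**The concern.** A mean over the eyes still present estimates the mean for all ITT eyes only if leaving is unrelated to pressure. An eye that leaves after Month 24 with a poor pressure already has readings that help predict its Month 36 value, and the planned estimate does not use them. A link between pressure and exit is possible on the documents' own terms: adverse events are a listed reason for early exit (Protocol 12.4), and an IOP at least 10 mmHg above baseline is a listed postoperative adverse event (Protocol 13.1.2, item z). How often the one leads to the other is not stated.

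The study is meant to give continued assurance of effectiveness as well as safety (Protocol 9.3). It has one arm, so a bias from attrition cannot cancel between groups and passes straight into the reported fall.

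**Working it through.** **1. The plan's own figures.** For n = 360 and a target of 7%, the largest count that rejects in the exact one-sided test is 17 events (exact alpha 0.0499). Power at a true 4% is 0.802, against 80% stated. 360 / (1 - 0.20) = 450. Both reproduce. If attrition reaches the allowed 20%, 450 - 360 = 90 eyes have no 36-month data.

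**2. Bias of the available-case mean.** With missing share d,

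overstatement of the fall = d x (mean change in leavers - mean change in completers),

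where a less negative change is a poorer result. At d = 0.20:

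| Gap (mmHg) | Overstatement (mmHg) |
|---|---|
| 0 | 0 |
| 1 | 0.2 |
| 2 | 0.4 |
| 3 | 0.6 |
| 4 | 0.8 |
| 5 | 1.0 |

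For a 2 mmHg gap the figure is 0.2 at d = 0.10 and 0.6 at d = 0.30. A negative gap (better-pressure eyes leave) reverses the sign.

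**3. What gap might arise.** The documents give no IOP change, SD, within-eye correlation or drop-out pattern, so these are assumptions: true change -5 mmHg, SD 4, correlation 0.4 to 0.8, drop-out after Month 6, 12 or 24 depending on the last recorded change with a logit slope of 0.1 to 0.2 per mmHg (odds ratios e^0.1 = 1.11 and e^0.2 = 1.22), and 20% missing at Month 36. Simulated overstatement: about 0.13 to 0.51 mmHg. By step 2 this corresponds to gaps of 0.13 / 0.2 = 0.65 to 0.51 / 0.2 = 2.55 mmHg. With slope 0 there is no bias.

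**4. Cross-check on a different setting.** True change -7, SD 4, Month 24 to Month 36 correlation 0.3 to 0.7, 20% drop-out depending on the Month 24 change, slope 0.1 to 0.3. Completer means: -7.09 to -7.54. A likelihood-type estimate using the Month 24 value: about -7.0.

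**5. If some early-exit IOPs are counted as Visit 8.** Suppose half the leavers have one, and it resembles their would-be Month 36 value. Leavers then make up 0.10 / 0.90 = 0.111 of the mean when they should make up 0.20. The overstatement is (0.20 - 0.111) x gap = 0.089 x gap, or about 0.06 to 0.23 mmHg for the gaps in step 3.

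**6. Scale.** With SD 4 and 360 eyes, the standard error is 4 / sqrt(360) = 0.21 mmHg. The low end in step 3 is below one standard error and the high end is over two.

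**The case against.** **The endpoint is descriptive.** There is no primary effectiveness endpoint, the secondary ones carry no hypotheses, and success rests only on the primary safety rate. This stands: no error rate or study decision changes.

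**Attrition will be visible.** Protocol 15.4.2.2 says "Summary statistics will be presented at all postoperative visits for which the endpoint data are collected", SAP 6.5.7 tabulates IOP and its change by visit, SAP 4.1 plans an accountability table, and Protocol 15.6 compares baseline characteristics, including IOP, by completion. These show the loss. They do not correct the Month 36 mean, because each visit uses its own available eyes.

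**Some leavers may be in the mean.** A reader might infer that every early leaver is excluded. The documents do not support that, because Protocol 12.4 seeks a Visit 8 assessment at early exit and the mapping is unstated. What can be said is that eyes with no IOP counted as Visit 8 are out.

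**Direction and size are assumed.** A reader might also infer that the reported fall will be too large. Nothing in the documents shows that poorer-pressure eyes leave more often, so the bias is conditional and could go the other way.

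**The model has its own assumption.** Its recovery of the true value in simulation is expected, since drop-out was generated from recorded IOPs, which is what missing at random requires. This is not evidence that the model would be unbiased in the trial. The available-case mean, however, needs the stronger condition that exit is unrelated to pressure.

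**Conclusion.** The point holds as a conditional one. As written, the Month 36 mean IOP change is an available-case mean, earlier pressures of eyes without a Visit 8 IOP are unused, up to 20% attrition is allowed for, and no missing-data analysis covers this endpoint. If exit depends on recorded pressure with poorer eyes leaving, the fall is overstated by about 0.13 to 0.51 mmHg under the assumptions in step 3, or roughly 3 to 10% of an assumed 5 mmHg fall. It is less if early-exit readings are counted as Visit 8, zero if exit is unrelated to IOP, and of opposite sign if better-pressure eyes leave. Only the reported effectiveness figure is affected. This is an inexpensive improvement to a descriptive result and does not threaten the study's conclusion on its primary endpoint.

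**What to change.** In SAP 5.1.2, keep the observed-case summary and add beside it:

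1. **A likelihood-based repeated-measures estimate** of Month 36 mean change with a 95% CI: visit as a factor, baseline IOP as covariate, unstructured covariance, scheduled visits from Month 1 or Month 3 onward (choose one in advance), and all ITT eyes with a baseline and at least one such IOP. The Day 1 and Week 1 readings fall in the perioperative period and are not needed. Like the planned summary, the model takes IOP as recorded, whatever the medication.
2. **A rule for early-exit IOPs:** analyse them at their actual time, and not as Month 36 when outside days 1050 to 1140. Apply it to the observed-case summary too.
3. **A delta-shift sensitivity analysis,** because the model assumes missing at random. Shifting the missing Month 36 values by delta moves the mean by the missing share times delta: at 20% missing, 1 mmHg moves it by 0.2 and 5 mmHg by 1.0.

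The cost is a few lines of SAP text and one standard model, with no new data. The downside is a little more analysis and reliance on missing at random, which is why both figures should be shown.

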8.2.2 Safety Endpoints

8.2.2.1 Primary Safety Endpoint

The primary endpoint is the rate of clinically relevant complications associated with CyPass Micro-Stent placement and stability as determined at 36 months. Specific device-related complications include:

- ≠ Failure to implant CyPass, defined as inability to successfully deploy or insert the CyPass.
- ≠ Clinically significant CyPass malposition, defined as CyPass positioning after deployment such that:
 - The device is not in the supraciliary space, or
 - There is a clinical sequela resulting from device position including, but not limited to:
 - ≠ Secondary surgical intervention to modify device position (eg, repositioning, proximal end trimming or explantation)
 - ≠ Corneal endothelial touch by device
 - ≠ Corneal edema leading to loss of BCDVA > 2 lines at the last postoperative visit, in comparison with preoperative BCDVA
 - ≠ Progressive ECL, defined as ongoing reduction in endothelial cell count of 30% or more relative to the screening ECD value, where 'ongoing reduction in endothelial cell count' is defined as losses continuing after Visit 5 (6 Month Follow-up)
 - ≠ Erosion of device through sclera
 - ≠ Device obstruction requiring secondary surgical intervention.

8.2.2.2 Secondary Safety Endpoints

All secondary safety endpoints will be evaluated at 36 months postoperatively.

- ≠ Rate of occurrence of sight-threatening adverse events including
 - Persistent (at time of study exit) BCDVA loss of 3 or more lines compared to best BCDVA achieved during the course of study
 - Endophthalmitis
 - Corneal decompensation
 - Retinal detachment
 - Severe choroidal hemorrhage or detachment
 - Aqueous misdirection
- ≠ The rate of ocular secondary surgical interventions (SSI)
- ≠ The rate of ocular SSIs associated with CyPass placement and stability

8.2.2.3

Other Safety Endpoints

All other safety endpoints will be evaluated at 36 months postoperatively.

- ≠ Increase from baseline IOP of 10 mmHg or greater at any time at/after 30 days postoperative
- ≠ BCDVA loss of 2 or more lines compared to screening (Visit 0)
- ≠ BCDVA loss of 2 or more lines in comparison with best recorded BCDVA at any postoperative visit
- ≠ Device movement, defined as a change by at least 1 in the number of CyPass rings visible (eg, from 1 ring to 2 rings or from 3 rings to 2 rings) that does not result in clinical sequelae (eg, secondary surgical intervention to modify device position, corneal endothelial touch by device, corneal edema leading to loss of BCDVA > 2 lines at the last postoperative visit in comparison with preoperative BCDVA, progressive endothelial cell loss, erosion of device through sclera, or device obstruction requiring secondary surgical intervention), and that is not attributable to any one or more of the following:
 - variations in gonioscopic viewing angle or illumination
 - changes in angle anatomy due to concomitant findings such as resolution of hyphema
 - changes in anterior chamber depth
 - development of focal peripheral anterior synechiae

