6 SCHEDULE OF VISITS

Procedure/Assessment	Visit 0 (-42 to -1 days) Screening	Visit 00 (Day 0) Surgery	Visit 1 (+1 day) 1 Day Follow-up	Visit 2 (+5 to 9 days) 1 Week Follow-up	Visit 3 (+21 to 35 days) 1 Month Follow-up	Visit 4 (+70 to 98 days) 3 Month Follow-up	Visit 5 (+150 to 210 days) 6 Month Follow-up	Visit 6 (+330 to 420 days) 12 Month Follow-up	Visit 7 (+690 to 780 days) 24 Month Follow-up	Visit 8 (+1050 to 1140 days) 36 Month Follow-up/Exit/Early Exit
Informed Consent	X									
Demographics	X									
Medical History	X	X	X	X	X	X	X	X	X	X
Concomitant Medications	X	X	X	X	X	X	X	X	X	X
Number of Ocular Hypotensive Medications	X ¹	X	X	X	X	X	X	X	X	X
Urine Pregnancy Test ²	X									
Inclusion/Exclusion	X									
Surgery ³ (with video)		X								
Manifest Refraction	X ¹			X	X	X	X	X	X	X
Monocular BCDVA	X ^{1,4}		X ⁵	X	X	X	X	X	X	X
Specular Microscopy ⁶	X ¹					X	X	X	X	X
Visual Field ⁷	X ¹							X	X	X
IOP (8:00 – 10:00 am)	X ¹		X	X	X	X	X	X	X	X
Slit Lamp Examination	X ¹		X	X	X	X	X	X	X	X
Gonioscopy (photographed)	X ¹	X	X	X	X	X	X	X	X	X
Fundus Examination	X ¹					X	X	X	X	X
Central Corneal Pachymetry	X ¹							X	X	X
UBM or OCT ⁸						(X)	(X)	(X)	(X)	(X)
Adverse Events	X	X	X	X	X	X	X	X	X	X
Device Deficiencies	X	X	X	X	X	X	X	X	X	X

¹ Conduct bilaterally at Visit 0 and in study eye only at postoperative visits, unless otherwise indicated.

² In women of child bearing potential only.

³ An Alcon observer may be present during surgery.

⁴ At Visit 0, if BCDVA better than 0.3 logMAR (> 85 letters read), repeat with BAT (Brightness Acuity Meter).

⁵ At Visit 1 (Day 1 Follow-up) BCDVA will be conducted as a pinhole test.

⁶ ECD may be requested in the fellow eye at follow-up on a case by case basis.

⁷ Visual field testing may be repeated between screening (Visit 0) and surgery (Visit 00), if needed.

⁸ UBM or OCT conducted if CyPass is not visible on Gonioscopy at two consecutive visits after Visit 3 (1 Month Follow-up). Images retained at site to demonstrate placement of CyPass.

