20. Remove the CyPass applier from the eye.
21. If resistance is encountered or adequate implantation is not achieved at the initial implant site, implantation at a location at least 2 clock hours away from any area of ciliary body disinsertion can be considered if there is no significant iris trauma, the CyPass Micro-Stent remains properly positioned on the guidewire, and adequate hemostasis and visualization can be maintained. Make sure that the position of the patient's head and the tilt of the microscope allow adequate gonioscopic visualization of the angle structures. Increase magnification and fine focus the microscope as needed. Additional viscoelastic tamponade may be needed to assure hemostasis and maintain visibility during CyPass Micro-Stent implantation. Align the curvature of the CyPass on the guidewire with the curvature of the sclera bordering the supraciliary space to reduce the possibility of encountering resistance during insertion.
22. Termination of the procedure should be considered after 2 failed attempts at device placement or if adequate visibility cannot be maintained during implantation.
23. Use gonioscopy to confirm CyPass Micro-Stent position. Optimal position of the CyPass Micro-Stent is when only the collar and the first retention ring are visible in the AC. Anterior positioning with more than 2 retention rings visible in the AC can be associated with corneal endothelial cell loss. Posterior positioning such that the collar is not visible can be associated with reduced device effectiveness.
 - a. If the CyPass Micro-Stent appears to be too anterior, use the guidewire tube of the CyPass applier to gently push the device deeper into the supraciliary space until it is optimally positioned. If the proximal end of the CyPass Micro-Stent appears to be too posterior, use a micro-forceps to grasp the CyPass Micro-Stent collar and gently pull it into the AC until the implant is optimally positioned. Do not use the irrigation/aspiration (I/A) tip for CyPass Micro-Stent positioning.
 - b. If proper placement cannot be achieved, implant removal should be considered. Use direct gonioscopy visualization and supplementary viscoelastic for safe removal.

24. Since retained viscoelastic can lead to elevated IOP in the early postoperative period, irrigate and aspirate viscoelastic from the AC, taking care to avoid I/A tip proximity to the CyPass Micro-Stent.

NOTE: The flow of irrigation fluid near the Micro-Stent may cause implant movement.

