- v. Choroidal effusion requiring surgical drainage
- vi. Suprachoroidal hemorrhage
- vii. BCDVA loss of ≥ 2 lines from the best postoperative BCDVA

z) Elevated mean IOP ≥ 10 mmHg than the qualifying baseline mean IOP at or after 1 month postoperative

aa) CyPass device obstructed by iris, vitreous, lens, fibrous overgrowth, fibrin, or blood

bb) CyPass device malposition – positioning after deployment such that the device is not in the supraciliary space

cc) CyPass device malposition – positioning after deployment such that there is a clinical sequela resulting from device position including, but not limited to:

- i. Secondary surgical intervention to modify device position (eg, repositioning, proximal end trimming or explantation)
- ii. Corneal endothelial touch by device
- iii. Corneal edema leading to loss of BCDVA > 2 lines at the last postoperative visit, in comparison with preoperative BCDVA
- iv. Progressive ECL, defined as ongoing reduction in endothelial cell count of 30% or more relative to the screening ECD value, where ‘ongoing reduction in endothelial cell count’ is defined as losses continuing after Visit 5 (6 Month Follow-up)
- v. Erosion of device through sclera
- vi. Device obstruction requiring secondary surgical intervention

dd) CyPass device dislodgement or movement, without sequelae, where device movement is defined as a change by at least 1 in the number of CyPass rings visible that is not attributable to variations in gonioscopic viewing angle or illumination, changes in angle anatomy due to concomitant findings such as resolution of hyphema, change in anterior chamber depth, or development of focal peripheral anterior synechiae

ee) CyPass device explantation associated with CyPass placement and stability

ff) CyPass device explantation NOT associated with CyPass placement and stability

gg) Unplanned ocular surgical reintervention associated with CyPass placement and stability

hh) Unplanned ocular surgical reintervention NOT associated with CyPass placement and stability (other than paracentesis to relieve pressure prior to 1 week postoperative or Nd:YAG capsulotomy)

- ii) Significant ptosis
- jj) Atrophy/phthisis
- kk) Wound dehiscence/leak (persistent aqueous leak or fistula formation)
- ll) Subconjunctival hemorrhage
- mm) Chronic pain in the study eye present greater than 3 months postoperative
- nn) Significant foreign body sensation at or after 3 months postoperative
- oo) IOL subluxation

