15.5.3.1 Statistical Hypotheses

There are no statistical hypotheses for the other safety endpoints.

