The rate of ocular SSIs associated with CyPass placement and stability	Adverse Event(s) SX	
Either of these two:
 
Postop - ee) CyPass device explantation associated with CyPass placement and stability
 
Postop - gg) Unplanned ocular surgical reintervention associated with CyPass placement and stability

Other Safety Endpoints		
Increase from baseline IOP of 10 mmHg or greater at any time at/after 30 days postoperative	Baseline: Intraocular Pressure_Glaucoma PostOp: Intraocular Pressure_Glaucoma_1	
BCDVA loss of 2 or more lines compared to screening (Visit 0)	Baseline: Visual Acuity_VAS PostOp: Visual Acuity_VAS_1	
BCDVA loss of 2 or more lines in comparison with best recorded BCDVA at any postoperative visit	Baseline: Visual Acuity_VAS PostOp: Visual Acuity_VAS_1	

Endpoint	CRF	Comments
Device movement, defined as a change by at least 1 in the number of CyPass rings visible (eg, from 1 ring to 2 rings or from 3 rings to 2 rings) that does not result in clinical sequelae (eg, secondary surgical intervention to modify device position, corneal endothelial touch by device, corneal edema leading to loss of BCDVA > 2 lines at the last postoperative visit in comparison with preoperative BCDVA, progressive endothelial cell loss, erosion of device through sclera, or device obstruction requiring secondary surgical intervention), and that is not attributable to any one or more of the following:	Adverse Event(s) SX	Postop - dd) CyPass device dislodgement or movement, without sequelae (as defined in the protocol)
variations in gonioscopic viewing angle or illumination		
changes in angle anatomy due to concomitant findings such as resolution of hyphema		
changes in anterior chamber depth		
development of focal peripheral anterior synechiae		

Endpoint	CRF	Comments
Additional Safety Assessments		
Adverse events (ocular and non-ocular)	Adverse Event(s) SX	
Device deficiencies	Device Deficiency	
Endothelial Cell Count	This will come from a dataset provided by the reading center, CIARC	
Slit lamp findings	Baseline: Slit Lamp Observations PostOp: Slit Lamp Observations_1	
Fundus examination (C/D ratio) and fundus findings	Baseline C/D: Fundus Exam PostOp C/D: Fundus Exam_1 Baseline observations: Fundus Observations PostOp observations: Fundus Observations_1	
Corneal pachymetry	Baseline: Corneal Thickness PostOp: Corneal Thickness_1	
Intraocular pressure	Baseline: Intraocular Pressure_Glaucoma PostOp: Intraocular Pressure_Glaucoma_1	

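### The ring-count definition of device movement misses one change: the collar passing out of, or back into, view in an eye with no ring showing

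*Protocol*

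**What the plan says.** Protocol 8.2.2.3 lists, among the other safety endpoints, "Device movement, defined as a change by at least 1 in the number of CyPass rings visible", provided that the change has no clinical sequelae and is not explained by viewing angle or illumination, angle anatomy, anterior chamber depth or focal synechiae. Adverse event item dd) in protocol 13.1.2 uses the same rule, again based on the ring count: "CyPass device dislodgement or movement, without sequelae, where device movement is defined as a change by at least 1 in the number of CyPass". SAP 6.4 repeats it and summarises the outcome as eyes affected over eyes in the ITT set. SAP Appendix C takes the data from the adverse event form, category dd): "CyPass device dislodgement or movement, without sequelae (as defined in the protocol").

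Position itself is described with two landmarks. In protocol 12.2.2.1, step 23, "Optimal position of the CyPass Micro-Stent is when only the collar and the first retention ring are visible in the AC". The same step ties more than two visible rings to possible endothelial cell loss, and adds: "Posterior positioning such that the collar is not visible can be associated with reduced device effectiveness".

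The schedule of visits (protocol section 6) provides for a stent that disappears from view: "UBM or OCT conducted if CyPass is not visible on Gonioscopy at two consecutive visits after Visit 3 (1 Month Follow-up"). It then states: "Images retained at site to demonstrate placement of CyPass".

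**The concern.** The study's stated subject is placement and stability, and this endpoint is the only defined rate of movement without sequelae. A ring count cannot fall below zero, yet the protocol describes a position further back than zero rings, with the collar also hidden, and attaches a possible consequence to it. If an eye already shows no ring, further sinking into that position leaves the count unchanged. Such an eye would be reported as stable, and a possible explanation for a poor IOP result at 36 months would not appear in the movement table.

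**Working it through.** No figure in the plan rests on this definition, so there is none to reproduce. The check applies the stated rule to the positions that the protocol itself distinguishes.

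**Inputs.** The rule is: movement if |change in rings visible| ≥ 1 (protocol 8.2.2.3, 13.1.2 dd), SAP 6.4). The positions come from protocol 12.2.2.1, steps 18 and 23: 3, 2, 1 or 0 rings with the collar visible, and 0 rings with the collar hidden. I take it from those steps that the collar is the last part to leave view as the stent sinks, so a hidden collar goes with 0 rings.

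**Absolute change in ring count for each pair of positions:**

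| From / to | 3 rings | 2 rings | 1 ring | 0 rings, collar visible | 0 rings, collar hidden |
|---|---|---|---|---|---|
| 3 rings | – | 1 | 2 | 3 | 3 |
| 2 rings | 1 | – | 1 | 2 | 2 |
| 1 ring | 2 | 1 | – | 1 | 1 |
| 0 rings, collar visible | 3 | 2 | 1 | – | **0** |
| 0 rings, collar hidden | 3 | 2 | 1 | **0** | – |

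There are 5 × 4 = 20 directed changes. Eighteen have a ring change of at least 1 and are counted. Two score 0 and are not: collar visible to hidden at 0 rings, and the reverse. Positions with more than 3 rings would add only counted changes. A stent at the target position (collar plus one ring) that sinks until nothing shows scores 1 and is counted.

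SAP 6.4 counts eyes, so an eye with any counted movement stays in the numerator even if its collar later disappears. The gap therefore concerns eyes whose only qualifying change is the collar change.

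**Does another part of the plan close the gap?**

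- Primary endpoint (protocol 8.2.2.1): requires the stent to be outside the supraciliary space or to cause a clinical sequela. A deeper stent can meet neither condition.
- UBM or OCT (protocol section 6): may be triggered when the stent is out of view, but the images stay at the site and no movement rule refers to them.
- Gonioscopy tables (SAP 6.5.4): abnormal findings by visit, with no within-eye change in collar visibility.
- SAP Appendix C: takes the endpoint from item dd) and refers back to the protocol definition, so no second criterion enters at the analysis stage.

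**Size.** Missed eyes = ITT eyes × share at 0 rings × share of those whose only qualifying change is collar visibility. The planned number of implanted eyes is 450. The documents give neither share, so the product cannot be evaluated.

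**The case against.** The strongest reply is that the gap is a corner case. The surgical steps aim for collar plus one ring, tell the surgeon how to adjust a stent that is too far back, and require position to be verified again after irrigation and aspiration. From that target, or from any position with more rings showing, sinking is counted. This stands, and it limits the point to eyes already at 0 rings.

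Second, such a case may be recorded elsewhere. Item dd) also names dislodgement, which has no definition, and the list of sequelae in the malposition definition is open-ended. A site could therefore report the case as dislodgement, or as malposition if it sees a sequela. Obstruction of the device has its own item, aa). Gonioscopy is done at every postoperative visit, with photographs of stent location from Visit 2, and reduced effectiveness would show in the IOP and medication results. This stands in part: the state is not unobserved, but capture in the movement rate is left to the site's discretion.

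Third, protocol 15.5.3.1 says: "There are no statistical hypotheses for the other safety endpoints". The outcome is descriptive and limited to movement without sequelae, so little turns on it. That also stands.

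Last, assessment detail is left to the Manual of Procedures and the gonioscopy form, neither of which is available here. Collar visibility may already be recorded. Even so, the written endpoint does not use it.

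A reader might infer that posterior movement is never counted, or that the reported rate as a whole leans toward anterior movement. The documents support neither. Posterior movement is missed only from 0 rings, the definition's own examples include a fall from 3 rings to 2, and the anterior change from collar hidden to collar visible is missed as well.

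**Conclusion.** The point holds in a narrow form. By its wording, the movement endpoint cannot register one change, in either direction: between 0 rings with the collar visible and 0 rings with the collar hidden. The consequence is a possible under-count of sequela-free movement, chiefly posterior movement in eyes already at 0 rings, into a position that the protocol says can be associated with reduced effectiveness.

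The size is unknown. It would be tempting to assume a share of the 450 eyes at 0 rings and quote the result, but that would count eyes in which a miss is possible, not missed events, and nothing in the documents supports a particular share. The primary endpoint, its 7% target, the exact test, the power and the sample size are unaffected. The conclusion rests on the collar being the last landmark to leave view, and on sites applying item dd) as written and not reporting these cases as dislodgement.

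**What to change.** In protocol 8.2.2.3, protocol 13.1.2 item dd) and SAP 6.4, keep the present rule (a change of at least 1 in the number of rings visible) and add: or a change in whether the collar is visible. Apply the same exclusions to both parts. SAP Appendix C then follows, since it points to item dd) and the protocol definition.

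Leave the ring count uncapped. An ordered scale that ends in a category of 3 or more rings would close the gap at the bottom but stop counting a change from 3 to 4 rings, should that many be able to show, which the present rule counts.

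Check that the gonioscopy form records collar visibility at each visit, and add the item if it does not. The cost is the change of wording and at most one form item, because gonioscopy is already scheduled at every postoperative visit. The reported movement rate may come out slightly higher.
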